#### Elderly patients

No dose adjustment is required for elderly patients (see [Section 5.2](#)).

#### Renal and hepatic impairment

No dose adjustment is required for patients with renal or hepatic impairment (see [Section 5.2](#)).

### **Administration**

Fasenra™ is administered as a subcutaneous injection by a healthcare professional. In line with clinical practice, monitoring of patients after administration of biologic agents is recommended.

Administer Fasenra™ into the upper arm, thighs, or abdomen. Do not administer into areas where the skin is tender, bruised, erythematous, or hardened ([Appendix D](#)).

### **Contraindications**

Fasenra™ is contraindicated in patients who have known hypersensitivity to benralizumab or any of its excipients.

### **Special warnings and special precautions for use**

Fasenra™ should not be used to treat acute asthma exacerbations.

Patients should be instructed to seek medical advice if their asthma remains uncontrolled or worsens after initiation of treatment.

Abrupt discontinuation of corticosteroids after initiation of Fasenra™ therapy is not recommended. Reduction in corticosteroid doses, if appropriate, should be gradual and performed under the supervision of a physician.

#### *Hypersensitivity reactions*

Hypersensitivity reactions (e.g. anaphylaxis, angioedema, urticaria, urticaria papular, rash) have occurred after administration of Fasenra™. These reactions may occur within hours of administration, but in some instances, have a delayed onset (ie, days).

In the event of a hypersensitivity reaction, Fasenra™ should be discontinued.

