### **Intervention Groups and Duration:**

Adult patients of severe asthma with eosinophilic phenotype requiring high dose of ICS plus LABA, who are prescribed Fasenra (benralizumab) 30 mg, subcutaneously, as an add-on therapy in line with the local prescribing information and are scheduled to initiate treatment with Fasenra (benralizumab) within 2 weeks will be enrolled in the study. The recommended dose of Fasenra (benralizumab) is 30 mg administered once every 4 weeks for the first 3 doses, and then once every 8 weeks thereafter by subcutaneous injection into the upper arm, thigh, or abdomen as per local prescribing information ([Appendix D](#)). The study drug, Fasenra (benralizumab), will be provided by AstraZeneca Pharma India Ltd. for the duration of the study.

The total study duration will be 24 weeks, including 16 weeks of study treatment.

- Screening duration: 2 weeks
- Study period: 24 weeks
  - Treatment duration (4 doses): 16 weeks (Day 1, Week 4, Week 8, and Week 16)
  - Post-treatment follow-up duration: 8 weeks (Week 24)

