### 4.2 Scientific Rationale for Study Design

This proposed Phase 4 single-arm study will fulfil the regulatory requirement as a postmarketing study to assess the safety of 30-mg benralizumab administered subcutaneously in Indian patients of severe asthma with eosinophilic phenotype who remain uncontrolled on high doses of ICS plus LABA. Owing to the recent marketing approval, there are no data available from real-life studies in the Indian population. Participants included in this study will be as per the indicated patient profile in the local prescribing information, specifically taking into consideration the contraindications, warnings, and special precautions for use.

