## **DISCONTINUATION OF STUDY INTERVENTION AND PARTICIPANT DISCONTINUATION/WITHDRAWAL**

### **7.1 Discontinuation of Study Intervention**

It may be necessary for a participant to permanently discontinue (definitive discontinuation) the study intervention. If study intervention is permanently discontinued, the participant will remain in the study to be evaluated for safety and effectiveness parameters. Evaluations and safety assessments at the time of discontinuation of study intervention may be performed as per study physician discretion.

Note that discontinuation from study intervention is NOT the same thing as a withdrawal from the study. Participants will be discontinued from benralizumab in the following situations:

- Participant is free to discontinue treatment at any point of time, without prejudice to further treatment (see [Section 7.2](#))
- Development of any study-specific criteria for discontinuation:
  - a. anaphylactic reaction to benralizumab requiring administration of epinephrine
  - b. development of helminth parasitic infestations requiring hospitalisation
  - c. intensive care unit admission with prolonged intubation and mechanical ventilation for asthma-related event
- Severe non-compliance to study protocol including if any dose of benralizumab is missed during the course of the study
- Eligibility requirement found not to be fulfilled (see [Section 5.1](#), [Section 5.2](#))
- Pregnancy (see [Section 8.2.5](#))
- Lost to follow-up

Before a decision to discontinue a participant from benralizumab instituted, the investigator should carefully consider whether continuation on benralizumab or discontinuation of benralizumab will be in the best interest of the patient, and whether the issue can be mitigated by postponing or skipping the dose. It is highly recommended that the AstraZeneca study physician be consulted before the benralizumab discontinuation transaction takes place. In case of safety concerns benralizumab administration may be immediately withheld until the final decision is made.

See the SoA for data to be collected at the time of intervention discontinuation and follow-up and for any further evaluations that need to be completed.

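### Protocol Section 7.1 and Appendix D conflict on stopping benralizumab after a hypersensitivity reaction, and the protocol does not say which governs (minor)

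*Protocol*

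**What the plan says.** **Appendix D (India label), Hypersensitivity reactions.** The label names anaphylaxis, angioedema, rash and urticaria (including the papular form) as reactions seen after the drug, some of them starting only days later. It then instructs: "In the event of a hypersensitivity reaction, Fasenra™ should be discontinued". No grade of severity or need for treatment is attached.

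**Protocol Section 7.1.** This section lists the situations in which a participant will be taken off benralizumab. The only allergic item is criterion (a): "anaphylactic reaction to benralizumab requiring administration of epinephrine". A later paragraph, not limited to any cause, asks the investigator to weigh continuing against stopping and to consider "whether the issue can be mitigated by postponing or skipping the dose". It strongly advises talking to the sponsor's study physician before treatment is stopped, and it lets a site hold back dosing at once for safety reasons while the decision is pending. Section 7.1 does not refer to Appendix D.

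**SAP Table 14.1.1.2.** The reasons for stopping study treatment repeat the narrow Section 7.1 criterion. There is no row for other hypersensitivity reactions and no general adverse-event row.

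**The concern.** Two instructions in the same protocol give different answers to one question: what to do at the next dosing visit after a reaction short of anaphylaxis treated with epinephrine. Angioedema, urticaria, rash, or anaphylaxis managed without epinephrine all call for stopping under Appendix D, and none meets a listed allergic criterion in Section 7.1.

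The gap is not confined to trivial events. Among its examples of important medical events, Appendix B gives angioedema treated with intravenous hydrocortisone, a type of event the protocol says should usually be classed as serious. Such an event would not trigger the mandatory stop in Section 7.1. Because onset can be delayed, observation at the site after injection does not settle the matter.

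What is at stake is mainly participant safety and consistency between sites. One site may stop under the label while another gives the next dose under Section 7.1's discretion. Reporting is affected less: a stop for urticaria would probably be tabulated under Other in Table 14.1.1.2.

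**Working it through.** **1. The texts side by side**

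| Event | Appendix D | Section 7.1 |
|---|---|---|
| Anaphylaxis treated with epinephrine | Stop | Stop (criterion a) |
| Anaphylaxis managed without epinephrine | Stop | No criterion; investigator weighs options |
| Angioedema, urticaria, rash | Stop | No criterion; investigator weighs options |

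**2. Does another section decide which governs?**

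- Section 4.2 refers to the label, "specifically taking into consideration the contraindications, warnings, and special precautions for use", but in describing which participants are included.
- The Synopsis and Section 4.3 tie the label to prescribing and dose. Section 6.2 cites Appendix D for dosage, preparation and administration.
- Exclusion 4 covers allergy known at entry, so the Section 7.1 item on unmet eligibility does not clearly reach a new reaction.
- Appendix D contraindicates the drug in known hypersensitivity, and Appendix B 4 says the sponsor would not normally support a re-challenge. Both lean against re-dosing. One is a contraindication and the other a causality guide; neither is written as a stopping rule.

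None of these says which text prevails.

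**3. The plan's own figure.** With z = 1.96, p = 0.10 and d = 0.05, n = z²p(1−p)/d² = 138.29, rounded up to 139 evaluable; 139/0.95 = 146.3, rounded up to 147 enrolled. Both figures reproduce, and this point does not affect them.

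**4. Scale**

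Inputs:

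- Treated participants, from the footnote to SAP Table 14.1.1.1: 154 − 10 screen failures − 6 eligible but not dosed = 138.
- Hypersensitivity rate: 3% in the USPI and SIROCCO columns of the Section 9.2 table, with a label range of 1% to 10%. The 3% is a literature figure; the sample size was planned at 10%.
- Doses: four, on Day 1 and at Weeks 4, 8 and 16, with follow-up to Week 24. Only a reaction before the Week 16 dose can be followed by another study dose.

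| | 1% | 3% | 10% |
|---|---|---|---|
| Any reaction: 138 × rate | 1.4 | 4.1 | 13.8 |
| Before last dose, even risk over time: × 16/24 | 0.9 | 2.8 | 9.2 |
| Before last dose, equal risk per dose: × 3/4 | 1.0 | 3.1 | 10.4 |

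Both timing splits are assumptions, since the documents give no onset data by dose. If every reaction came early, the 3% figure would be about 4. If the 3% had accrued over 48 weeks and scaled with time (also an assumption; the documents do not state the period behind it), it would be 4.14 × 16/48 = 1.4.

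These figures cap the number who could be re-dosed. Some would be stopped anyway, and the documents give no basis for estimating how many would not.

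**5. Effect on the primary endpoint.** Stopping counts towards the percentage with adverse events leading to discontinuation or modification; re-dosing on schedule does not. At 3%, site practice could move that percentage by at most 3% × 16/24 = 2.0 to 3% × 3/4 = 2.25 percentage points under the two timing assumptions. The reactions are reported as adverse events by Preferred Term either way.

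**The case against.** The strongest reply is that a label-contrary dose is left open only if Section 7.1 is read in isolation. Appendix D is part of the protocol, and Appendix A requires conduct in accordance with the protocol. A participant who has just reacted has a known hypersensitivity, which the label contraindicates.

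The Section 7.1 list is not stated to be exclusive, and items (a) to (c) are called study-specific, so they can be read as additions to the label. Stopping for other adverse events is plainly foreseen: action taken is recorded for every event, Section 8.2.3 mentions laboratory or vital-sign changes that lead to discontinuation, and a primary endpoint counts such stops. Dosing may also be withheld at once. Finally, the disposition counts (124 completed + 20 discontinued + 10 screen failures = 154) suggest that dosing is over, so no amendment could now protect anyone.

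Most of this stands, and it lowers the severity. It does not remove the conflict. The mandatory list is narrower than the label, the discretion paragraph expressly invites thought of continuing, and no sentence ranks the two texts.

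Two reporting arguments also stand. Table 14.3.1.5 would show a stop for urticaria by Preferred Term, and Table 14.1.1.1 has an adverse-event reason for participants who leave the study. The Table 14.1.1.2 gap is therefore one of presentation.

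**Conclusion.** The point holds as a minor one: two stated instructions conflict, and the protocol does not say which governs.

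A reader might infer more, in three ways that the documents do not support:

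- **That the protocol directs or authorises re-dosing against the label.** Section 7.1 requires no further dose, advises consultation and allows withholding. A site that follows Appendix D breaches nothing in it.
- **That participants were re-dosed after a reaction.** The documents hold no event data. At the 3% literature rate the ceiling is about 3 of 138 under the two timing assumptions, about 1 to 10 over the 1% to 10% range, and the actual number may be zero.
- **That the primary safety results are compromised.** Only one component is exposed, by about 2 percentage points at most at 3% under those assumptions, and the events are reported regardless.

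If dosing is complete, the remaining value lies in showing whether any such re-dose occurred. In a safety study required for Indian approval, that is worth one listing.

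**What to change.** **If any participant is still to be dosed:**

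- Replace criterion (a) in Section 7.1 with: *any hypersensitivity reaction to benralizumab (e.g. anaphylaxis, angioedema, urticaria, rash), per Appendix D*.
- State that the postpone-or-skip paragraph does not override this criterion.
- Add the matching reason row to SAP Table 14.1.1.2.

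The cost is one criterion, one sentence and one table row, plus a few more discontinuations: about 3 to 4 of 138 at the 3% rate, some of them for mild rash. Because the criterion is a reaction to benralizumab, an unrelated rash would not force a stop. Under Section 7.1, those who stop treatment remain in the study for safety follow-up.

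**If dosing is complete:** leave the protocol unchanged. Fix the Preferred Terms that count as hypersensitivity before the listing is run, then produce one listing of those TEAEs with action taken (Listing 16.3.1.2) and later dose dates (Listing 16.1.6.1). Do not rely on Table 14.1.6 for doses, because its programmer note covers Visits 1 to 3 and the Week 16 dose is at Visit 4. The cost is one merged listing from data already collected, with no effect on participants.

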#### *Parasitic (Helminth) Infection*

Eosinophils may be involved in the immunological response to some helminth infections. Patients with known helminth infections were excluded from participation in clinical trials. It is unknown if Fasenra™ may influence a patient's response against helminth infections.

Treat patients with pre-existing helminth infections before initiating therapy with Fasenra™. If patients become infected while receiving treatment with Fasenra™ and do not respond to antihelminth treatment, discontinue treatment with Fasenra™ until infection resolves.

#### **Effects on ability to drive and use machines**

Fasenra™ has no or negligible influence on the ability to drive and use machines.

#### **Special precautions for storage**

Store in a refrigerator (2°C to 8°C). Store the prefilled syringe in the original package to protect from light. Do not freeze.

#### **Nature and contents of container**

One mL solution in a sterile, single-use prefilled syringe made from type I glass with a staked 29 gauge ½ inch stainless steel needle, rigid needle shield, and Fluorotec-coated stopper in a passive safety device.

Fasenra™ is available in a pack containing 1 single dose prefilled syringe.

#### **Instructions for use, handling and disposal**

Do not shake. Do not use if frozen.

[figure not shown]
#### **Instructions for administration**

Before administration, warm Fasenra™ by leaving carton at room temperature. This generally takes 30 minutes. Administer within 24 hours or discard into sharps container.

**Instructions for Prefilled Syringe with Needle Safety Guard**

[figure not shown]
Refer to figure below to identify the prefilled syringe components for use in the administration steps.

**Figure:**

**Do not touch the needle guard activation clips** to prevent premature activation of the needle safety guard.

1     **Grasp the syringe body**, not the plunger, to remove prefilled syringe from the tray. Check the expiration date on the syringe. Visually inspect Fasenra™ for particulate matter and discolouration before administration. Fasenra™ is clear, colourless to yellow, and may contain translucent or white to off-white particles. Do not use Fasenra™ if liquid is cloudy, discoloured, or if it contains large particles or foreign particulate matter. The syringe may contain a small air bubble; this is normal. **Do not** expel the air bubble before administration.

2	 Do not remove needle cover until ready to inject. Hold the syringe body and remove the needle cover by pulling straight off. Do not hold the plunger or plunger head while removing the needle cover or the plunger may move. If prefilled syringe is damaged or contaminated (for example, dropped without needle cover in place), discard and use a new prefilled syringe.
3	Gently pinch the skin and insert the needle at the

	
recommended injection site (ie, upper arm, thigh, or abdomen)

4
 	
Inject all of the medication by pushing in the plunger all the way until the plunger head is completely between the needle guard activation clips. This is necessary to activate the needle guard.

5
 	
After injection, maintain pressure on the plunger head and remove the needle from the skin. Release pressure on the plunger head to allow the needle guard to cover the needle. Do not re-cap the prefilled syringe.

6
 
Discard the used syringe into a sharps container.
	

## Appendix E Coronavirus Disease-19 Vaccination Guidance

In response to the current pandemic and approval/emergency use authorization (EUA) of novel SARS-CoV-2 (COVID-19) vaccines, AstraZeneca has developed the following guidance for benralizumab (Fasenra) trials:

- The trials continue as per approved Clinical Study Protocol.
- Ongoing participants in clinical trials may receive an approved/EUA COVID-19 vaccine when made available to them.
- Vaccine administration must be at least 7 days apart from IP injection, longer interval is advised when possible. If needed, IP dose can be re-scheduled to allow for sufficient interval prior/post COVID vaccination.
- Subsequent IP dose should be given a different location from the vaccine.
- Patients who received COVID-19 vaccination prior to the study start should not be randomized until >30 days after the last vaccine dose.
- COVID vaccination must be recorded on Concomitant Medication module in eCRF clearly indicating the vaccine brand. That applies to any COVID-19 vaccine received prior to or during the study.
- Use of experimental and/or non-approved and /or non-authorised COVID-19 vaccines is disallowed.
- The decision to vaccinate should be based on the risks and benefits for each individual patient and on what is in the patient's best interest according to the Investigator's clinical judgement.
- Any questions should be addressed to the study Medical Team through the QA log, or direct communication if urgent.

## Appendix F Abbreviations

Abbreviation or special term	Explanation
ADA	antidrug antibody
ADR	adverse drug reaction
AE	adverse event
CI	confidence interval
COPD	chronic obstructive pulmonary disease
CRO	contract research organisation
ECG	electrocardiogram
EDC	electronic data capture
ER	Emergency Room
eCRF	electronic case report form
EOS	End of Study
FEV1	forced expiratory volume in 1 second
GCP	Good Clinical Practice
GINA	Global Initiative for Asthma
ICS	inhaled corticosteroid
ICF	informed consent form
ICH	International Council for Harmonisation
IEC	Independent Ethics Committee
IL-5	interleukin-5
IL-5Ra	interleukin-5 receptor alpha subunit
IMP	Investigational Medicinal Product
IRB	Institutional Review Board
KM	Kaplan-Meier
LABA	long-acting beta-agonist
OCS	8.1. steroid
PI	Package Insert
Pre-BD	prebronchodilator
Post-BD	postbronchodilator
SAE	serious adverse event
SD	standard deviation
SAP	statistical analysis plan
SmPC	Summary of product characteristics
SoA	schedule of activities

Abbreviation or special term	Explanation
TEAE	treatment-emergent adverse event
USPI	United States Prescribing Information

LABA	long-acting beta-agonist
OCS	8.1.Oral corticosteroid
PI	Package Insert
Pre-BD	prebronchodilator
Post-BD	postbronchodilator
SAE	serious adverse event
SD	standard deviation
SAP	statistical analysis plan
SmPC	Summary of product characteristics
SoA	schedule of activities
TEAE	treatment-emergent adverse event
USPI	United States Prescribing Information

Document Title:	Document ID:	BP04-01
Statistical Analysis Plan	Version Number:	3.1
	Effective Date:	25-Nov-2021

1. INTRODUCTION

The purpose of this document is to provide a description of the statistical methods and procedures to be implemented for the analysis of data from D3250C00093 study. This document is based on protocol V 1.0, 09 Mar 2021. The statistical planning and conduct of analysis of the data from this study will follow the principles defined in relevant International Council on Harmonisation (ICH)-E9 guidelines. Any change from the planned analysis as described in the protocol, are detailed here, and any differences described here supersede the analysis as presented in the protocol.

2. Study Objective and Design

2.1 Study Objective

2.1.1 Primary Objective

- To Assess the safety and tolerability of Fasenra (Benralizumab) in adult patients of Severe asthma with eosinophilic phenotype over a period of 24 weeks.

2.1.2 Secondary Objective

- To assess the effectiveness of Fasenra (benralizumab) in adult patients of severe asthma with eosinophilic phenotype over a period of 24 weeks

2.2 Study Description

2.2.1 Study Design

This is a Phase 4, single-arm, prospective, multicentre, interventional study, designed to assess the safety, tolerability, and effectiveness of benralizumab in adult patients of severe asthma with eosinophilic phenotype in India. The study is planned to meet the post approval commitment as a regulatory requirement.

Ten centres across India will participate in this study. The investigators will be pulmonologists or chest physicians treating asthma patients. Informed consent will be obtained from all the patients at screening before any study-related procedures are performed. Adult patients of severe asthma with eosinophilic phenotype, who are prescribed benralizumab as an add-on therapy by the treating physician, will be enrolled in the study.

The total study duration will be 24 weeks, including 16 weeks of study treatment, and 8 weeks follow-up.

- Screening duration: 2 weeks
- Study period: 24 weeks
 - Treatment duration (4 doses): 16 weeks (Day 1, Week 4, Week 8, and Week 16)
 - Post-treatment follow-up duration: 8 weeks (Week 24)

Participants will be maintained on their currently prescribed therapies including ICS-LABA therapy(ies), throughout the study duration.

Document Title:	Document ID:	BP04-01
Statistical Analysis Plan	Version Number:	3.1
	Effective Date:	25-Nov-2021

Study population will include adult (18 to 75 years of age) male or female patients who have severe asthma with eosinophilic phenotype requiring high dose of ICS and LABA.

Each participant should meet all the inclusion criteria and none of the exclusion criteria to be eligible for the study.

Under no circumstances can there be exceptions to this rule. Participants who do not meet the entry requirements are screen failures

“Enrolled” means a participant's, or their legally acceptable representative's, agreement to participate in a clinical study after completion of the informed consent process. Prospective approval of protocol deviations to recruitment and enrolment criteria, also known as protocol waivers or exemptions, is not permitted.

This proposed Phase 4 single-arm study will fulfil the regulatory requirement as a postmarketing study to assess the safety of 30-mg benralizumab administered subcutaneously in Indian patients of severe asthma with eosinophilic phenotype who remain uncontrolled on high doses of ICS plus LABA. Owing to the recent marketing approval, there are no data available from real-life studies in the Indian population. Participants included in this study will be as per the indicated patient profile in the local prescribing information, specifically taking into consideration the contraindications, warnings, and special precautions for use.

The study will enrol patients who have been prescribed benralizumab as per the local prescribing information. The recommended dose is 30 mg administered once every 4 weeks for the first 3 doses, and then once every 8 weeks thereafter by subcutaneous injection into the upper arm, thigh, or abdomen by the study physician. Four doses of benralizumab will be administered as part of the study.

